12.6.2.2. Parameters for Adverse Events Collection

All nonserious AEs and SAEs will be recorded on the AE eCRF. SAEs will also be immediately reported to the Sponsor safety representative in accordance with Section [12.5.5](#).

Nonserious and SAEs will be documented in the clinical database with the highest severity documented during the duration of each serious or nonserious episode. Each AE is to be documented in the eCRF with reference to date of onset, severity, relationship to study drug, treatment of event, and outcome.

All AEs are to be followed up until resolution or a stable clinical endpoint is reached, as determined by the Investigator. Changes in AEs and resolution dates are to be documented in the eCRF.

Participants will be instructed by the Investigator to report AEs at each study visit. All volunteered, elicited, and observed AEs are to be recorded. A consistent methodology of nondirective questioning should be adopted for eliciting AE information at all participant evaluation timepoints. Examples of nondirective questions include the following:

- “How are you feeling?”
- “How have you felt since your last clinic visit?”

- “Have you had any new or changed health problems since you were last here?”
- “Have you taken any new medications since your last visit?”

The following considerations should also be made regarding AE and SAE reporting:

- All medical and psychiatric conditions present at screening (i.e., conditions present before the AE reporting period) will be considered preexisting conditions and documented in the medical history eCRF. A preexisting condition is not to be reported as an AE. If a preexisting condition worsens during the study treatment period, the event should be reported as an AE. Planned hospitalization for a preexisting condition, or a procedure required by the protocol, without serious deterioration in health, is not considered an SAE.
- Diagnostic and therapeutic noninvasive and invasive procedures, such as surgery, should not be reported as AEs. A medical condition for which an unscheduled procedure was performed, should however be reported if it meets the definition of an AE. For example, an acute appendicitis, and not the appendectomy, should be reported as the AE.
- Clinically significant abnormal laboratory findings (e.g., hematology, clinical chemistry [including glucose], coagulation, and urinalysis) or other abnormal assessments (e.g., in ECG results and vital signs), meeting the definition of an AE or SAE, that are detected during the study or are present at baseline and significantly worsen following the start of the study will be reported as AEs or SAEs. The Investigator will exercise his/her medical and scientific judgment in deciding whether an abnormal laboratory finding, or other abnormal assessment is clinically significant.

Special situations are non-standard medical conditions that provide valuable information (e.g., clinical, safety) about a medicinal product, even when special situations do not occur in association with an AE or medical condition. Special situations, defined in this protocol as events of accidental overdose, medication error, and drug misuse, are not in and of themselves AEs but may result in AEs. Each AE associated with a special situation should be recorded in the AE eCRF. If the associated AE fulfills seriousness criteria, the event should be reported to the Sponsor immediately (i.e., no more than 24 hours after learning of the event).

In the event of an accidental overdose, medication error or drug misuse special situation, the Investigator should:

- Inform the Medical Monitor immediately.
- Closely monitor the participant for an AE/SAE and laboratory abnormalities.
- In the event of an accidental overdose: document the quantity of excess dose in the eCRF.

12.6.3. Assessment of Event Severity

The Investigator will use the National Cancer Institute (NCI) Common Terminology Criteria for Adverse Events (CTCAE) version 5.0 to describe the severity of AEs. AEs not listed in the CTCAE will be graded as follows:

Grade 1	Mild; asymptomatic or mild symptoms; clinical or diagnostic observations only; intervention not indicated.
Grade 2	Moderate; minimal, local, or noninvasive intervention indicated; limiting age-appropriate instrumental activities of daily living (ADL). ADL refers to preparing meals, shopping for groceries or clothes, using the telephone, managing money, etc.
Grade 3	Severe or medically significant but not immediately life-threatening; hospitalization or prolongation of hospitalization indicated; disabling; limiting self-care ADL. Self-care ADL refers to bathing, dressing & undressing, feeding self, using the toilet, taking medications, and not bedridden.
Grade 4	Life-threatening consequences; urgent intervention indicated.
Grade 5	Death related to the AE.

12.6.4. Relationship to Study Treatment

Specific guidelines for classifying AEs by relationship to study treatment are given in [Table 8](#).

Table 8 Classification of Adverse Events by Relationship to Study Treatment

NOT RELATED: There is not a reasonable possibility that the administration of the study intervention caused the event, there is no temporal relationship between the study intervention and event onset, or an alternate etiology has been established.
RELATED: The AE is known to occur with the study intervention, there is a reasonable possibility that the study intervention caused the AE, or there is a temporal relationship between the study intervention and event. Reasonable possibility means that there is evidence to suggest a causal relationship between the study intervention and the AE.

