12.6.1.2. Adverse Reaction

A response to a medicine in humans which is noxious and unintended, and which occurs at any dose, and which can also result from overdose, misuse, or abuse of a medicine. Response to a medicinal product in this context means that a causal relationship between the medicinal product and an AE is at least a reasonable possibility.

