### 18.2 Analysis

An overall summary will be presented as the number of participants within each of the event type categories described in the sub-sections below, including the incidence of TEAEs by SOC and preferred term, unless otherwise specified. Both number of participants, number of mentions (i.e., events) and percentage will be provided.

All TEAEs will be summarized by treatment sequence and period of event as follows:

- All AEs,
- Grade  $\geq 3$  AEs
- AEs related to study treatment, including related Grade  $\geq 3$  AEs,
- All adverse drug reactions, and
- SAEs

All AEs will be listed by participant, along with information regarding onset, duration, relationship, and severity to study treatment, action taken with study treatment, treatment of event, and outcome as captured in the EDC.

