### 18.2.3 Drug-related TEAEs

Classification of Adverse Events by relationship to study treatment:

- **NOT RELATED:** There is not a reasonable possibility that the administration of the study intervention caused the event, there is no temporal relationship between the study intervention and event onset, or an alternate etiology has been established.
- **RELATED:** The AE is known to occur with the study intervention, there is a reasonable possibility that the study intervention caused the AE, or there is a temporal relationship between the study intervention and event. Reasonable possibility means that there is evidence to suggest a causal relationship between the study intervention and the AE.

The incidence of all drug-related TEAEs will be presented by SOC and preferred term for each treatment of event. “*Treatment of event*” will be derived as the last treatment exposed to prior to the onset of the AE.

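### The RELATED and NOT RELATED definitions in Protocol Table 8 and SAP 18.2.3 overlap with no rule of precedence, so counts of drug-related events rest on an inconsistent rule

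*Protocol*

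**What the plan says.** Protocol 12.6.4 gives investigators specific guidelines for judging relationship, in Table 8. Each category is a list of alternatives.

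- RELATED has three limbs. The first is "The AE is known to occur with the study intervention". The other two are "there is a reasonable possibility that the study intervention caused the AE, or there is a temporal relationship between the study intervention and event".
- NOT RELATED also has three limbs. The first is "There is not a reasonable possibility that the administration of the study intervention caused the event". The other two are "there is no temporal relationship between the study intervention and event onset, or an alternate etiology has been established".

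One closing sentence explains a term: "Reasonable possibility means that there is evidence to suggest a causal relationship between the study intervention and the AE". Neither document says which category wins when an event meets limbs of both.

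SAP 18.2.3 repeats both definitions and builds a table on them: "The incidence of all drug-related TEAEs will be presented by SOC and preferred term for each treatment of event". SAP 18.2 also plans a summary of "AEs related to study treatment, including related Grade" ≥3, and Protocol 14.5 plans the same. Both sections list adverse reactions as a separate line. Protocol 12.6.1.2 defines an adverse reaction by a different test, namely that "a causal relationship between the medicinal product and an AE is at least a reasonable possibility".

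**The concern.** Timing alone is enough for RELATED, and an established other cause alone is enough for NOT RELATED. An event that follows the injection and is then traced to something else therefore satisfies both definitions. Two assessors could both comply with Table 8 and enter different answers for the same event.

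At stake is the meaning of the related-event counts in the first clinical study of this product, where safety is a secondary objective. There is also a question of consistency. An event classed as RELATED through timing alone, without evidence of causation, would not qualify as an adverse reaction under Protocol 12.6.1.2. The recorded AE items in Protocol 12.6.2.2 include the relationship to study drug but no separate adverse-reaction item, so how the two summary lines are meant to differ is not stated.

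**Working it through.** The plan gives no figure to reproduce, so the check is a logical one on the printed definitions.

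**Inputs** (Protocol Table 8, same wording in SAP 18.2.3), each taken as yes or no:

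- K: the event is a known effect of the intervention
- R: there is a reasonable possibility of causation
- T: there is a temporal relationship
- E: an alternate etiology is established

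**Rules as printed**

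- RELATED = K or R or T
- NOT RELATED = (not R) or (not T) or E

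**Count over the 2 × 2 × 2 × 2 = 16 combinations**

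- RELATED only requires R and T present and E absent, with K free: 2 combinations.
- NOT RELATED only requires K, R and T all absent, with E free: 2 combinations.
- Neither: 0.
- Both: 16 − 2 − 2 = 12.

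The plainest case, an event after dosing with an established other cause and nothing else pointing to the drug (T = 1, E = 1, K = 0, R = 0), is among the 12. Among the 8 combinations with T = 1, all 8 meet RELATED and 6 also meet NOT RELATED.

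**Do kinder readings, or a partial repair, remove the overlap?**

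| Reading or change | Both | RELATED only | NOT RELATED only | Neither |
|---|---|---|---|---|
| As printed | 12 | 2 | 2 | 0 |
| Assume E rules out R (12 feasible combinations) | 8 | 2 | 2 | 0 |
| Read NOT RELATED as requiring all three limbs | 1 | 13 | 1 | 1 |
| Delete only the timing limb of RELATED | 10 | 2 | 4 | 0 |
| Let R alone decide | 0 | 8 | 8 | 0 |

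The second reading still leaves the plainest case in both categories. The third removes that case, but it goes against the printed *or*, still leaves one combination in both categories, and leaves one in neither. Deleting the timing limb alone is not enough. Of the options checked, only a single deciding criterion gives exclusive and exhaustive categories.

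**Does other text settle it?** The closing sentence of Table 8 explains the reasonable-possibility limb only; it neither restricts the timing limb nor sets an order. The rule in Protocol 14.5 that uses the occurrence with the closest association chooses among repeat occurrences of an AE. It does not say how a single event is classified.

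These are counts of logical combinations, not expected shares of adverse events.

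**The case against.** The strongest reply is that little depends on this. The relationship is recorded for each AE in the eCRF (Protocol 12.6.2.2), and treatment of event is defined in SAP 18.2.3, so the tables can be produced. Investigators are blinded (Protocol 8.3.2), there is one center, and the design is a crossover. Uneven reading of Table 8 would therefore make absolute counts unstable, but no mechanism is shown by which it would favor one product. All TEAEs are summarized whatever their causality, and every AE is listed with its relationship, so nothing is hidden. The side effects named in Protocol 4.2 (allergic reactions, hypoglycemia, hypokalemia, weight gain) meet RELATED as known effects without the timing limb. All of this stands and limits the consequence. None of it supplies a precedence rule.

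A reader might also infer three stronger things that the documents do not support.

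- **That most events during the clamps are affected.** Up to 54 × 3 = 162 clamps are planned, but that counts clamps, not events, and no AE rate is given. The alternate etiology must be established, not merely possible. AE collection starts with study treatment on Day 1 (Protocol 12.6.2.1), so events before the first dose fall outside it.
- **That SAE reporting is compromised.** Protocol 12.6.5 sends every SAE within the reporting window to the sponsor safety representative within 24 hours, with no causality condition.
- **That Table 8 contradicts the adverse-reaction definition.** Protocol 12.6.1.2 defines a different term, and a broader category can sit beside a narrower one. The fair statement is that the timing limb uses a different causality standard and the link between the two is not explained.

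**Conclusion.** The point holds as a conflict inside a stated rule. Table 8 and SAP 18.2.3 allow the same event to be RELATED and NOT RELATED, and neither document says which prevails. The drug-related TEAE table and the related Grade ≥3 summary can be produced, but the judgement behind each entry has no single rule.

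The size is modest. The effect is confined to descriptive, secondary safety summaries recorded by blinded investigators. The primary PK/PD equivalence tests and the sample size do not depend on it. The number of events involved cannot be estimated from the documents. The conclusion rests on reading *or* as printed; assuming that an established other cause rules out a reasonable possibility narrows the overlap to 8 of 12 combinations but does not remove it. The correction is worth making because it is cheap and determines which events enter the related-event summaries.

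**What to change.** Reword Protocol Table 8 and SAP 18.2.3 together so that one criterion decides:

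- RELATED: there is a reasonable possibility that the study intervention caused the event.
- NOT RELATED: there is no such reasonable possibility.
- Known effects, timing and alternate etiology are evidence to weigh in that judgement, and none of them is sufficient alone for RELATED.

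This brings the overlap from 12 of 16 combinations to 0, leaves no event unclassified, and puts Table 8 on the same causality standard as Protocol 12.6.1.2. Both definitions have to change, since deleting only the timing limb leaves 10 of 16.

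The cost is a wording change in two places and brief site training, with no new data collection. The small downside is that fewer events would count as related on timing alone.

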12.6.5. Serious Adverse Event Reporting

Any SAE occurring during the course of the study within the defined AE reporting window, must be immediately reported to the appropriate Sponsor safety representative (PrimeVigilance) within 1 calendar day (i.e., within 24 hours) of the investigational site's initial awareness of the event. The study SAE Report Form, provided by the Sponsor, will be utilized for reporting safety information to the Sponsor safety representative and completed in English. For fatal or life-threatening treatment-emergent SAEs, where important or relevant information is missing, active follow up will be undertaken immediately by the Investigator.

A post-study AE or SAE is defined as any event that occurs outside of the AE/SAE monitoring period. Investigators are not obligated to actively monitor AEs or SAEs of such study participants. However, if the Investigator learns of any AE or SAE, including a death, at any time after a participant has completed the study, and it is considered reasonably related to the study treatment, the Investigator should promptly notify the Sponsor safety representative within 24 hours of becoming aware of the event.

Investigators or other site personnel will inform the Sponsor safety representative of any follow-up information on a previously reported SAE within 1 calendar day (i.e., within 24 hours) of the investigational site's awareness of the new information. All SAEs will be followed until satisfactory resolution, until the Investigator deems the event to be chronic, or

the participant is stable. Other supporting documentation of the event may be requested by the Sponsor or Sponsor safety representative and should be provided by the Investigator as soon as possible.

The Sponsor will notify regulatory authorities and participating Investigators of any reportable SAEs for NKF-INS(A), US-NovoLog[®], and EU-NovoRapid[®]) in an expedited fashion in accordance with local requirements. Where required and in accordance with local requirements, the Sponsor will ensure unblinding of subject treatment assignment for the purposes of reporting the event to regulatory authorities. IRBs/IECs will be promptly notified, in accordance with local regulations, of all reportable SAEs involving risk to human participants. Where reportable SAEs are identified for referenced products, i.e., US-NovoLog[®] and EU-NovoRapid[®], the Sponsor will ensure the product manufacturer is notified within the same expedited timelines as regulatory authorities.

For further guidance on the definition of an SAE, see Section [12.5.1.3](#).

12.7. Drug-Induced Liver Injury Monitoring

For new elevations in transaminases greater than $2 \times$ the upper limit of normal (ULN) in participants with normal baseline values, repeat measurement will be performed within 48 hours. If elevations persist, participants will be evaluated for other causes of transaminase elevations and with tests of hepatic function. If no other cause is found, then the participants will be monitored closely and the drug discontinued as per the recommendations in the FDA Guidance for Industry – Drug-Induced Liver Injury: Premarketing Clinical Evaluation ([US FDA, 2009](#)).

The participant should be followed until resolution of symptoms or signs in the following situations:

- Alanine aminotransferase (ALT) or aspartate aminotransferase (AST) $>8 \times$ ULN.
- ALT or AST $>5 \times$ ULN for more than 4 days during the 7-day treatment period.
- ALT or AST $>3 \times$ ULN (and total bilirubin $>2 \times$ ULN or international normalized ratio [INR] >1.5).
- ALT or AST $>3 \times$ ULN with the appearance of fatigue, nausea, vomiting, right upper quadrant pain or tenderness, fever, rash, and/or eosinophilia ($>5\%$).

12.7.1. Pregnancy

After administration of study treatment, any known cases of pregnancy in female partners of male study participants will be reported until the male participant completes or withdraws from the study and within 90 days of their exposure to study treatment. The Investigator may arrange counseling for pregnant female partners of male study participants by a specialist to discuss the risks of continuing with the pregnancy and the possible effects on the fetus. The pregnancy will be reported immediately by faxing/emailing a completed pregnancy report to the Sponsor safety representative (or designee) within 24 hours of knowledge of the event. The pregnancy will not be processed as an AE/SAE; however, the Investigator must follow up with female partners of male study participants until completion of the pregnancy, and must assess the outcome in the shortest possible time, but not more than 30 days, after completion of the pregnancy. The Investigator should notify the Sponsor (or designee) of the pregnancy outcome by submitting a follow-up pregnancy report. If the outcome of the pregnancy involved spontaneous or therapeutic abortion (any congenital anomaly detected in

an aborted fetus is to be documented as an SAE), stillbirth, neonatal death, or congenital anomaly, the Investigator will report the SAE by faxing/emailing a completed pregnancy report form to the Sponsor safety representative (or designee) within 24 hours of knowledge of the event. Any pregnancy in female partners of male study participants will be followed to term, and the status of the mother and child will be reported to the Sponsor after delivery.

Contraception guidance is provided in [Appendix 1](#).

12.7.2. Accidental Overdose, Medication Error, or Drug Misuse

Accidental overdose, medication error, and drug misuse, hereafter collectively referred to as “special situations,” are defined as follows:

- Accidental overdose: accidental administration of a drug in a quantity that is higher than the assigned dose.
- Medication error: accidental deviation in the administration of a drug. In some cases, a medication error may be intercepted before administration of the drug.
- Drug misuse: intentional deviation in the administration of a drug that does not qualify as drug abuse.

Cases of accidental overdose, drug misuse, or medication error without manifested signs or symptoms are not considered AEs. Adverse events associated with an overdose will be documented according to Section [12.5.5](#). SAEs associated with overdose should be reported according to the procedure outlined in Section [12.6.2](#). All cases of overdose (with or without associated AEs) will be documented on the eCRF.

13. OTHER ASSESSMENTS

13.1. Euglycemic Clamp Procedure

NKF-INS(A), US-NovoLog® and EU-NovoRapid® will be administered using a euglycemic glucose clamp at targeted blood glucose concentrations. The euglycemic glucose clamp will be conducted using a manual clamp technique, which will continuously monitor the subject's blood glucose and administer GIR to maintain blood glucose close to the target blood glucose concentration. The clamp procedure will be initiated, maintained, and terminated, in accordance with the site SOPs. The participant's blood glucose will be maintained within a pre-defined target window per site SOP and clinical judgment for the participant by manually adjusting the GIR.

Blood samples will be collected at pre-specified intervals before and up to 12 hours after dosing for measurement of blood glucose, serum insulin, and C-peptide as shown in the schedule of assessments ([Table 3](#)).

14. STATISTICAL ANALYSIS

An SAP will be prepared after the protocol is approved. The SAP will provide further details regarding the definition of analysis variables and analysis methodology to address all study objectives. The SAP will serve as a complement to the protocol and supersedes it in case of differences.

The statistical evaluation will be performed using R version 4.0 or higher. All data will be listed, and summary tables and figures will be provided. Summary statistics will be presented by treatment group, to the extent possible. For continuous variables, data will be summarized with the number of participants (N), arithmetic mean, SD, median, minimum, and maximum by treatment group. Geometric mean and CV% will be presented as appropriate, by treatment group. For categorical variables, data will be tabulated with the number and proportion of participants for each category by treatment group.

